**TABLE 3: SOLICITED ADVERSE EVENTS**

Type	Event
Local AEs (Immunisation site)	Pain Tenderness Erythema / Discolouration Warmth Itching Swelling
Systemic Clinical AEs	Abnormally raised temperature Chills / rigors Myalgia / flu-like general muscle aches Malaise Excess fatigue Headache Nausea / Vomiting Abdominal Pain Diarrhoea Sore throat

The events will be graded according to **Appendix 1**.

**Relationship to the product**, the assumption is that any of these solicited events starting within 7 days of an immunisation are at least possibly related. If the onset is beyond 7 days, the event will be recorded on the adverse event CRF and a relationship determined by the investigator or delegate.

#### **12.3.5 NON-SOLICITED ADVERSE EVENTS**

Non-solicited AEs starting from the first vaccination until the final safety visit (Week 28) will be captured and reported on the adverse event CRF. When making a non-solicited AE enquiry, staff should ask a non-leading question such as 'how have you been feeling?'

#### **12.3.6 FOLLOW-UP OF ADVERSE EVENTS AND PREGNANCY**

The Investigator will make every effort to monitor all adverse events, regardless of severity, until resolution or stabilisation in order to report this on the CRF (see section 15.1.1) during the trial.

After the database is locked and the trial is closed, any additional information about adverse events or pregnancy that comes to the attention of an investigator should be reported by email to the Principal Investigator.

### 12.3.7 SERIOUS ADVERSE EVENTS

A serious adverse event is defined in section 13.1. These will be collected throughout the entire study period.

All serious adverse events should be reviewed by the PI and discussed at the next TMG call. The assessment should include consideration of whether or not to discontinue dosing or to withdraw a participant from the trial.

For all serious adverse events, the investigator will complete the serious adverse event form as soon as becoming aware of the event and, within 24 hours, will:

- Email it to the Coordinating Centre (Clinical Trials Manager) as well as notify by phone the form has been sent
- Email it to the Imperial Joint Research Compliance Office

### 12.4 PROCEDURES FOR ASSESSING IMMUNOGENICITY

Samples (indicated below) will be collected at the timepoints specified in Table 2 and transferred to the [name] Laboratory for analysis.

**Cervico-vaginal secretion samples** will be collected from female participants using a commercially available, self-inserted menstrual cup, at the time points indicated in Table 2, except at visits when female participants are menstruating in which case cervico-vaginal secretions will not be collected. In the case of light spotting, a sample **will** be collected.

**Rectal secretion samples** will be collected from male and female participants. Absorbent swabs will be held against the rectal wall for 2 minutes. Should a participant not wish to have a proctoscopy the swab may be inserted by the nurse or doctor or self-inserted by the participant, 3 cm into the anal canal.

**Semen samples** will be collected from male participants whilst within the clinical trials unit or brought into the clinic following donation at the time points indicated in Table 2. Semen samples should be donated following 24 hours of sexual abstinence, and produced  $\leq 2$  hours before being handed to clinic staff.

**Nasal secretion samples** will be collected from male and female participants using nasal synthetic absorptive matrix at the time points indicated in Table 2.

#### Rectal biopsies (Part 2 only)

Participants may opt out of this procedure. Rectal biopsies will be collected from the rectal walls of male and female participants with a Sarratt biopsy forcep (or similar sterile, single-use disposable device). Biopsies may be taken on the left and/or right rectal wall at each scheduled time-point, from sites selected by the doctor performing the procedure such that high quality samples can be safely taken. The time-points are sufficiently spaced to allow the mucosa to heal completely between biopsies.

#### Blood and Serology Specimens

For measurement of antibodies in serum, 6ml peripheral venous blood will be collected into an appropriate blood collection tube, and then processed to obtain serum.

**Blood for Immunogenicity assays requiring PBMC**

For assessment of T-cell responses, 40-50ml ml of peripheral venous blood will be collected into tubes containing sodium heparin as an anti-coagulant, mixed by inverting gently several times and then processed to obtain PBMC which will be frozen and stored for future batch immunogenicity analysis.

**12.5 PROCEDURES FOR ASSESSING AD4 SHEDDING**

Rectal swabs will be used to collect stool samples from male and female participants and the samples assessed for viral shedding by a polymerase chain reaction (PCR) assay.

**12.6 CRITERIA FOR STOPPING TREATMENT GROUPS OR WHOLE TRIAL**

All trial immunisations will be put on hold in the event of a SAR or two severe ARs, and in the event of every subsequent SAR or severe AR.

In the event of a SAR, the PI should notify the sponsor within 24 hours of becoming aware, and the PI will arrange for any necessary expert reviews to take place.

Further immunisations will be put on hold until the review is completed.

A component of any expert review will be to consider whether or not further immunisations should be discontinued in the individual, and/or the trial.

If immunisations are put on hold, the TMG will determine whether or not to call an unscheduled meeting of the Independent Data Monitoring Committee (IDMC) to review the safety data, and whether or not to hold further immunisations until this has taken place. If an unscheduled IDMC is warranted, the Sponsor will be informed and the IDMC asked to make a recommendation to the Principal Investigator and the Sponsor about continuing further immunisations.

At any time if the study is put on hold (for example following the occurrence of a SAR) the Regulatory authority has to be informed of the temporary halt and a substantial amendment with relevant data has to be submitted to the MHRA for approval in case a decision to resume dosing is taken. The Sponsor reserves the right to stop the whole trial at any time.

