## 11.5 DOSE MODIFICATIONS, INTERRUPTIONS & DISCONTINUATIONS

There are no planned modifications to dose, other than discontinuation.

The schedule may be modified if a participant has symptoms or signs on the day of scheduled immunisation, and the investigator considers it best to defer the immunisation. The participant will be asked to return for review within the window period of a scheduled immunisation.

The Principal Investigator may decide to permanently discontinue dosing in a participant who has received one or more vaccinations, if it is deemed that continuing might compromise the participant's wellbeing or interfere with the achievement of the trial's objectives. Participants will be encouraged to continue to attend trial visits for sampling and safety monitoring.

Discontinuation of dosing is essential following a grade 3 or 4 clinical or laboratory event (confirmed on examination or repeat testing respectively) which is considered possibly, probably or definitely related to the vaccine and which did not resolve within 72 hours. All participants will be followed up for the duration of the study and samples will be collected at the allotted times.

Dosing must be discontinued in participants who become pregnant or HIV infected.

Participants may decide to discontinue dosing. They will be encouraged to provide a reason, and to remain in follow-up. If the participant explicitly states their wish not to contribute further data to the study, the PI should be informed in writing.

Both the PI and the coordinator centre should be informed as soon as possible if a participant chooses to stop receiving vaccines or to withdraw from the trial, and within 1 working day of a decision being taken to discontinue a participant when that decision is informed by an adverse event (**Section 13.1**).

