##### *Safety and Tolerability:*

- Proportion of participants with severe or greater (Grades 3-4) adverse reactions during the study
- Proportion of participants with vaccine-related serious adverse events (SAEs) throughout the study period

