## 24 APPENDICES

## APPENDIX 1 ADVERSE EVENTS GRADING

All AEs (except those listed in the tables below) should be graded according to the following criteria:

- **Symptom not experienced (Grade 0)**
- **Mild (Grade 1):** No interference with daily activity
- **Moderate (Grade 2):** Some interference with daily activity
- **Severe (Grade 3):** Prevents daily activity
- **Potentially life-threatening (Grade 4):** Emergency treatment or hospitalisation

REACTION	GRADE 1	GRADE 2	GRADE 3	GRADE 4
Fever (oral temperature)	38.0 – 38.4	38.5 – 38.9	39.0 – 40.0	≥ 40.1
Tachycardia (bpm)*	101 – 115	116 – 130	> 130	Emergency treatment or hospitalisation
Bradycardia (bpm)**	50 – 54	45 – 49	< 45	Emergency treatment or hospitalisation
Hypertension (mm Hg) Systolic	141 – 150	151 – 155	> 155	Emergency treatment or hospitalisation
Hypertension (mm Hg) Diastolic	91 – 95	96 – 100	> 100	Emergency treatment or hospitalisation
Hypotension (mm Hg)*** Systolic	85 – 89	80 – 84	< 80	Emergency treatment or hospitalisation
Redness (cm) (greatest single diameter)	2.5 – 5	5.1 – 10	≥ 10.1	Necrosis or exfoliative dermatitis
Swelling (cm) (greatest single diameter)	2.5 – 5	5.1 – 10	≥ 10.1	Necrosis

\* At rest

\*\* When resting heart rate is between 60 – 100 beats per minute. Use clinical judgement when characterising bradycardia among some healthy subject populations, for example, conditioned athletes.

\*\*\* Only if symptomatic (e.g. dizzy/ light-headed)

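### Two wording errors touch the trial-wide hold: 13.3.3 labels every related non-solicited event an SAR, and 12.6 says severe without adding Grade 4

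*Protocol*

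**What the plan says.** **The hold.** Protocol 12.6 states "All trial immunisations will be put on hold in the event of a SAR or two severe ARs". For the period after the first hold it extends the trigger with the words "and in the event of every subsequent SAR or severe AR". No grade number appears. The same section requires the regulator to be told of any halt, and a substantial amendment to be approved before dosing resumes. The SAP contains no hold rule.

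**What makes a reaction an SAR.** Table 4 (13.1) sets the seriousness criteria: death, actual risk of death at the time, hospitalisation, disability, congenital anomaly, or another important medical condition. Table 5 (13.3.3) maps possible, probable and definite relationship to AR. The sentence in 13.3.3 that introduces Table 5 maps those three categories to SAR instead. It covers non-solicited events only. Solicited events starting within 7 days of a vaccination are ARs automatically under Table 4.

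**How severity is worded elsewhere.** The primary safety endpoint in 14.2.1 is "Proportion of participants with severe or greater (Grades 3-4) adverse reactions during the study", and SAP 10.1.2 repeats it. Section 11.5 says "Discontinuation of dosing is essential following a grade 3 or 4 clinical or laboratory event", limited to events "considered possibly, probably or definitely related to the vaccine and which did not resolve within 72 hours".

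**The scale.** Appendix 1 opens with "All AEs (except those listed in the tables below) should be graded according to the following criteria". In that general list the top two entries begin "Severe (Grade 3" and "Potentially life-threatening (Grade 4". The laboratory table heads Grade 3 as severe and Grade 4 as extreme. The clinical table holding fever, redness and swelling shows grade numbers without words.

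**The concern.** One SAR is enough to stop all immunisations, so the definition of SAR is part of the stopping rule. If 13.3.3 is followed as written, a single mild, possibly related, non-solicited complaint is an SAR. It would hold the trial, start the regulatory steps in 12.6, and be labelled a serious reaction when it is not serious.

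The 12.6 wording errs in the other direction. If severe means Grade 3 exactly, two non-serious Grade 3 reactions stop dosing but two non-serious Grade 4 reactions need not. After the first hold, a single non-serious Grade 4 reaction need not stop it again. A worse event would then count for less than a milder one, in a Phase I trial of a replicating vector whose protocol (7.8) reports no clinical data for it. Section 11.5 does not fill the gap: it acts on one participant, and only if the event has not resolved within 72 hours.

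**Working it through.** The plan gives no hold probability to reproduce. The check is a comparison of text, followed by an illustration on assumed rates.

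**1. The 13.3.3 conflict**

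| Related, non-serious, non-solicited event | Label | Effect under 12.6 |
|---|---|---|
| Sentence in 13.3.3 | SAR | one event holds the trial |
| Table 5, with Table 4 seriousness | AR | counts only if severe; two needed for the first hold |

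The two lines of the table cannot both be right. Section 13.3.1 has seriousness judged first, against Table 4, so the Table 5 line fits the rest of the protocol.

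**2. Counts towards the first hold under 12.6**

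| Events | Severe read as Grade 3 only | Severe or greater |
|---|---|---|
| Two non-serious Grade 4 ARs | 0 | 2 (hold) |
| One Grade 3 and one non-serious Grade 4 AR | 1 | 2 (hold) |

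**3. Which events are affected**

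Protocol Table 3 lists 6 local + 10 systemic = 16 solicited events. Three have their own Appendix 1 row (fever, redness, swelling), leaving 16 − 3 = 13 on the general scale.
- For the 13, Grade 4 is emergency treatment or hospitalisation. Admission makes the reaction an SAR. Emergency treatment alone will often do so through the important-medical-condition note to Table 4.
- For redness and swelling, Grade 4 is necrosis (redness also exfoliative dermatitis).
- Only fever has a purely numerical Grade 4, at 40.1 or above.

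Related laboratory and other non-solicited events are outside this gap as the text stands, because 13.3.3 makes them SARs. If 13.3.3 alone were corrected, a related non-serious Grade 4 laboratory value would fall into the gap.

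**4. Illustration**

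Part 1 dosing visits: 48 × 3 = 144. All rates are assumptions, visits and event types are treated as independent, and no genuine SAR occurs. For a rate p per visit, P(at least 1) = 1 − (1 − p)^144, and P(at least 2) = 1 − (1 − p)^144 − 144p(1 − p)^143.

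Non-serious Grade 4 ARs:

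| Rate per visit | P(at least 1) | P(at least 2) |
|---|---|---|
| 0.01% | 0.014 | 0.0001 |
| 0.05% | 0.070 | 0.0025 |
| 0.1% | 0.134 | 0.009 |

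Effect of the 12.6 edit on P(at least 2 counted ARs), adding those Grade 4 rates to a Grade 3 rate:

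| Grade 3 rate | Grade 3 only | with 0.01% | with 0.05% | with 0.1% |
|---|---|---|---|---|
| 0.5% | 0.163 | 0.168 | 0.188 | 0.214 |
| 1% | 0.423 | 0.428 | 0.447 | 0.471 |
| 2% | 0.785 | 0.788 | 0.797 | 0.808 |

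From unrounded values, the rise runs from 0.2 to 5.2 percentage points.

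Effect of both edits on the chance of any first hold. Assume solicited Grade 3 at 1%, solicited non-serious Grade 4 at 0.05%, and related non-serious non-solicited events at q per visit, 5% of them Grade 3-4. For q = 1%:
- As written: 1 − 0.99^144 × P(at most 1 at 1%) = 1 − 0.2352 × 0.577 = 0.864.
- 12.6 edit only: 1 − 0.2352 × 0.553 = 0.870.
- Both edits: P(at least 2) at 1% + 0.05% + 0.05 × 1% = 1.10%, which is 0.471.

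The same three figures are 0.719, 0.731 and 0.459 for q = 0.5%, and above 0.999, above 0.999 and 0.655 for q = 10%. With q = 1% and a Grade 3-4 share of 2% or 10% instead of 5%, the rate under both edits is 1.07% or 1.15% and the last figure 0.457 or 0.494.

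**The case against.** The strongest reply is that neither slip would mislead a competent site. In a safety trigger, severe naturally sets a floor, and 11.5 and 14.2.1 both treat Grades 3 and 4 together. Appendix 1 applies its worded labels only to events not in its tables, so the fever row, the clearest example, has no severe category that could exclude Grade 4. The note to Table 4 says that reactions which may jeopardise the subject, or need intervention to prevent a serious outcome, should be considered serious, and one SAR suffices for a hold. Section 13.2 adds 24-hour reporting of certain important events, and the sponsor may stop the trial at any time. For 13.3.3, staff using Table 5 would classify correctly anyway.

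Most of this stands, and it limits the point to a clarification. It does not remove it. The remaining safeguards rest on judgement or act on one participant, whereas the hold is meant to be automatic. And the 13.3.3 sentence contradicts its own table within an operative rule.

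A reader might infer that Grade 4 was deliberately left out, or that Grade 4 reactions in general escape the hold. No text excludes Grade 4, and section 3 of the working shows how few events remain. A reader might also take the fall from 0.864 to 0.471 as the size of the 12.6 problem. It comes from correcting 13.3.3; in that illustration the 12.6 edit alone moves the figure by 0.6 points.

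**Conclusion.** Both wording errors are real, and the point is minor. The 13.3.3 sentence is plainly wrong against Table 5 and Table 4, and taken literally it makes the hold far too sensitive to mild non-solicited events. If the site already follows Table 5, it has no practical effect. The omission in 12.6 leaves a narrow literal gap, mainly a solicited fever of 40.1 or above without admission and not judged medically important. Describing a Grade 3 fever as severe is itself an inference from the endpoint wording and the laboratory headings.

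The design of the hold is not at fault. It would also go too far to say that the vaccine-related SAE endpoint will be inflated: that would require the 13.3.3 label to override the Table 4 seriousness assessment, which the documents do not say. The probabilities only illustrate direction and scale. The 5.2-point upper end needs one non-serious Grade 4 reaction for every five Grade 3 reactions (0.1% against 0.5%), which is hard to credit for so small a set of events.

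**What to change.** Make the two edits together.
- In 13.3.3, classify possibly, probably or definitely related events as AR, and as SAR only if they also meet the Table 4 seriousness criteria.
- In 12.6, write *two severe or greater (Grade 3-4) ARs* for the first trigger and *every subsequent SAR or severe or greater (Grade 3-4) AR* for later ones.

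The edits are paired because correcting 13.3.3 alone would leave related non-serious Grade 4 laboratory values outside a literal reading of 12.6.

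The cost is protocol wording only, with no new data or procedure. A few more Grade 4 reactions would count towards a hold. Against the literal text, mild related non-solicited events would no longer trigger one, and the first hold for non-serious Grade 3-4 non-solicited reactions would need two events instead of one.

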**12.7 EARLY STOPPING & FOLLOW-UP**

If a participant chooses to discontinue their trial treatment, they should always be followed up providing they are willing, that is, they should be encouraged to not leave the trial. If they do not wish to remain on trial follow-up, however, their decision must be respected and the participant will be withdrawn from the trial completely. The trial team should be informed of this in writing using the appropriate documentation.

If the medical data collected during the participant's participation in the trial are kept for research and analysis purposes, they must remain anonymised. Consent for future use of stored samples already collected can be refused when leaving the trial early (but this should be discouraged and should follow a discussion).

## 12.8 WITHDRAWAL OF PARTICIPANTS

Withdrawal means stopping all further visits.

The reason(s) for withdrawal should be recorded in the CRF.

All participants are free to withdraw from the trial at any time, for any reason, without affecting their future medical care. The PI may decide to withdraw a participant if the investigator deems that continuing might compromise participant wellbeing or interfere with the achievement of the trial's objectives.

Participants who are withdrawn due to an adverse event (AE) will be followed-up until the event has stabilised.

Withdrawn participants who have received any immunisations will be asked to undergo the procedures scheduled for the primary endpoint visit (Visit 9; Week 26), with the addition of an HIV test and (women only) a pregnancy test.

### 12.8.1 Policy for Replacing Withdrawals

As the number of participants per group is small and hence each participant is essential to the study we will replace those that withdraw from the study before completion of the week 26 visit. Based on previous experience we would expect potential withdrawal of 10-20% of participants, predominantly as a result of changes in their personal circumstance that prevents visit attendance. Should we observe a >20% drop out in any group based on perceived safety or tolerability (i.e. more than 1 participant per group), further replacement will be determined by the TMG.

## 12.9 END OF TRIAL DEFINITION

The trial will be closed when all participants have made their final visit (Week 48; Visit 11), the data entered into the database and all queries resolved and the database locked. There will be a final monitoring/closeout visit to the clinical site between the last visit and the database lock.

## 13 SAFETY REPORTING

The principles of ICH GCP require that both investigators and sponsors follow specific procedures when notifying and reporting adverse events or reactions in clinical trials. These procedures are described in this section of the protocol. **Section 13.1** lists definitions, **section 13.3** describes details of the responsibilities of the institutions/investigators.

### 13.1 DEFINITIONS

The definitions of the EU Directive 2001/20/EC Article 2 based on the principles of ICH GCP apply to this trial protocol. These definitions are given in Table 4.

**TABLE 4 TYPES OF ADVERSE EVENTS AND DEFINITIONS**

Type of Event	Definition
Adverse Event (AE)	
Any untoward medical occurrence in a patient or clinical trial subject to whom a medicinal product has been administered including occurrences that are not necessarily caused by or related to that product.
 
The Principal Investigator will use the following criteria when deciding whether to report a laboratory parameter that falls outside the normal range according to the local laboratory guidelines as an adverse event:
 
 
- If it is clinically significant and Grade 1 (or above) according to the grading system in Appendix 1 the abnormal result will be recorded as an AE
 
-
 

Adverse Reaction (AR)	
Any untoward and unintended response to an investigational medicinal product related to any dose administered.
 
'Related' means possibly, probably or definitely as defined below.
 
All solicited adverse events which start within 7 days of a vaccination will be automatically classified as an adverse reaction.

1 An abnormal result will be deemed to be clinically significant if any of the following apply:

- The test result is associated with relevant accompanying symptoms
- Additional diagnostic tests or medication are indicated

- As a consequence of the test result, an immunisation is delayed or further immunisations are discontinued
- The investigator considers the result to constitute an adverse event for any other reason

**TABLE 4 TYPES OF ADVERSE EVENTS AND DEFINITIONS CONTINUED**

Type of Event	Definition
Unexpected Adverse Reaction (UAR)	An adverse reaction, the nature or severity of which is not consistent with the information about the medicinal product in question set out in the Summary of Product Characteristics (SPC) or Investigator Brochure (IB) for that product.
Serious Adverse Event (SAE) or Serious Adverse Reaction (SAR) or Suspected Unexpected Serious Adverse Reaction (SUSAR)	
Respectively any adverse event, adverse reaction or unexpected adverse reaction that:
 
 
• Results in death
 
• Is life-threatening*
 
• Requires hospitalisation or prolongation of existing hospitalisation**
 
• Results in persistent or significant disability or incapacity
 
• Consists of a congenital anomaly or birth defect
 
• Is another important medical condition***
 
 
Notes:  'A threat to life' refers to an event or reaction in which the patient was at risk of death at the time of the event; it does not refer to an event or reaction which hypothetically might have caused death had it been more severe.
 
If an AE is serious and unexpected and considered possibly, probably or definitely related to study product according to the classification below then it meets the criteria for a SUSAR and should be reported accordingly.

\*The term life-threatening in the definition of a serious event refers to an event in which the patient is at risk of death at the time of the event; it does not refer to an event that hypothetically might cause death if it were more severe, for example, a silent myocardial infarction.

\*\*Hospitalisation is defined as an inpatient admission, regardless of length of stay, even if the hospitalisation is a precautionary measure for continued observation. Hospitalisations for a pre-existing condition, that has not worsened or for an elective procedure do not constitute an SAE.

\*\*\* Medical judgement should be exercised in deciding whether an AE or AR is serious in other situations. The following should also be considered serious: important AEs or ARs that are not immediately life-threatening or do not result in death or hospitalisation but may jeopardise the subject or may require intervention to prevent one of the other outcomes listed in the definition above; for example, a secondary malignancy, an allergic bronchospasm requiring intensive emergency treatment, seizures or blood dyscrasias that do not result in hospitalisation or development of drug dependency.

